Subjects who sign the trial subject consent form and participate in the trial but do not finish will be eliminated. The elimination of a subject can be determined at any time during the trial. Withdrawal of consent by the subject will also be considered as an elimination and the reason for the withdrawal of consent must be clearly recorded. Furthermore, if an adverse event and/or a serious adverse event occurs during the trial, the corresponding subject will be immediately eliminated from the trial.

8) Safety Evaluation Criteria (Including Side Effects), Evaluation Methods, and Reporting Methods

Data Safety Monitoring Plan (DSMP)

According to existing research results, this trial is expected to be low risk because of the possibility and

severity of risk and discomfort which could occur in this in trial. The principal investigator is planned to continuously monitor for this risk and discomfort. Safety monitoring for this research will be conducted during every visit through an oral interview, a physical exam, laboratory tests, *et cetera*. If any of these results correspond to an SAE, it will be reported to the IRB.

- If there are any deviations from the protocol, the investigator will report major deviations to the IRB within 15 days of the point at which he or she becomes aware of the deviation and if there are minor deviations, the investigator will gather incidents of minor deviations and report them to the IRB at least once a year.
- Adverse events and all other information relating to safety will be reported in a safety information summary report. If there are incidents related to safety, a summary of the accumulated non-individual data should be compiled and reported at least once every 6 months in the form of a summary.

- Cases related to danger to the research subjects or other persons in which the case is judged to be an unexpected problem or in which it is life threatening should be reported to the IRB within 7 days and within 15 days for all other cases.
- The principal investigator or the subinvestigator will collect data and safety information, examine major efficacy evaluation endpoints, and conduct continuous monitoring every 6 months after the start of research.

9) Data Analysis and Statistical Analysis Methods

- Descriptive statistics (mean and standard deviation) are used to describe continuous variables of baseline demographic and biochemical parameters, and counts with percentages are presented for categorical variables of baseline demographic and biochemical parameters.
- The efficacy and safety analyses were based on the full analysis set population consisting of all the patients who received the investigational drug at least once.
- The demographic characteristics of subjects were analyzed using ANOVA for the continuous variables and the chi-squared (χ^2) test for the categorical variables.
- Efficacy endpoints at week 12 and week 24 were analyzed using ANCOVA model with Bonferroni (baseline value as a covariate) for continuous variables and Pearson chi-square test adjusted by Bonferroni for categorical variables.
- Missing data, which is an unavoidable occurrence in prospective studies, will be substituted for using the last observation carried forward (LOCF) method.
- A p value <0.05 will be considered to indicate statistical significance and the SPSS (Statistical Package for Social Sciences) Version 25.0 will be used for statistical analysis

10. Measures for the Protection of Research Subject Safety

1) Fundamental Measures to Ensure Research Ethicality

The Declaration of Helsinki (Revised 2013) and the ICH-GCP will be followed.

IRB approval is scheduled to be received before the start of this research. At the start of research after IRB approval, the research objectives and process will be sufficiently explained to the research subjects. An examination consent form will be received from persons who understand these and voluntarily choose to participate.

Prior to the start of the trial, the trial investigator must acquire the written approval of the institutional review board of the relevant trial institutions and/or regulatory commissions regarding the conduct of the trial and must send a copy to Takeda ([contact]). If alteration of the trial is necessary, the investigator must acquire the written approval of the institutional review board of the relevant trial institutions and/or regulatory commissions regarding the conduct of the trial and must send a copy to Takeda ([contact]).

As the research relates to human subjects, the investigators must register this trial at clinicaltrials.gov and any other relevant institutions if necessary.

2) Research Subject Consent Process

<Research Subject Consent Process>

The supervising investigator and joint investigators must receive written consent from each research subject or his or her representative prior to participation in the trial. Consent must be recorded in writing. The research subject or his or her representative must sign and date the consent form and the person who led the discussion about consent must also sign and date the consent form. A copy of the signed and dated consent form must be sent to the research subject before they participate in clinical research. Before acquiring consent, an explanation of the research methods, the trial drugs, and the expected discomfort, risk, and benefit to research subject must be explained in such a way that these

can be sufficiently understood. After an explanation is given to the research subjects, the subjects must be allotted sufficient time to consider participating in the trial. After such time (expected to take more than 30 minutes), the consent process will proceed. Research subjects will voluntarily participate in the research according to their own volition. Even if they do not participate in the research, they can receive future treatment and will therefore not incur any disadvantage. The explanation of the research must be provided in language such that the research subject or his or her representative will be able to understand. All written information supplied to the research subjects such as the initial consent form, later revised consent forms, etc., must receive the approval of the IRB prior to use. If new information is obtained which could relate to the willingness of the research subjects who will continue to participate in this clinical trial, the research subjects must be promptly notified and this notification must be given in writing.

3) Research Subject Compensation Plan

The research subjects will be paid a transportation fee of 30,000 won.

4) Research Subject Personal Information Protection Measures

Strict personal information and non-disclosure procedures will be used to prevent the disclosure of any information pertaining to the research subject's medical records to any persons other than the investigators. The Institutional Review Board does not infringe on the personal information of patients and the personal information of the patients will not be infringed upon in the process of monitoring or investigating the research. A patient's medical records can be directly inspected for a data credibility verification, which may be compulsory at the requirement of a relevant law or regulatory authority. To ensure that other persons or other institutions will not be able to obtain any information relating to the research subjects, information which could directly identify a subject such as his or her name or other information will not be included on samples or medical records. To protect personal information, only the research subject number will be used on samples, and the research subject's name or other information which could directly identify the research subject will not leave the research institution. Moreover, the key which connects personal information to the research subject codes will be stored in a separate file under the supervision of the supervising investigator to protect personal information. Furthermore, for any results obtained from this research, a designated key supervisor who did not participate in this research will store the key file, and before any report is provided to an investigator, all identifiable information must be removed by encoding to protect personal information. Medical records relating to this research will be stored safely for a maximum of 10 years for future research, records, and follow-ups. After this time, the research subject's clinical specimens will be disposed of biologically and records relating to the research will be also disposed of.

5) Plan for Supplemental Protective Measures if Vulnerable Research Subjects Are Included

Not applicable

11. Plan for the Storage and Disposal of Human Biological Materials

Human biological materials obtained through the research will be stored until the end of the research period and disposed of in accordance with the relevant laws.

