Research Subjects	Randomly assigned patients with type 2 diabetes who are first starting their treatment or patients who have fail with the metformin treatment and must change their medicine.		
Number of Research Subjects	A total of 198 patients (66 blinded patients for each treatment group) will participate in the trial and receive treatment for 6 months.		
Trial Drug/Medical Device	
 
 Alogliptin 25mg	
 
 Glimepiride	
 
	Alogliptin 25mg	Glimepiride
Alogliptin 25mg			
Glimepiride			

	Alogliptin 25mg +pioglitazone 15mg
Usage and Dose	
 • Alogliptin's nonproprietary name is alogliptin benzoate and is an oval-shaped yellow tablet. A 25 mg dose of this medication is administered once a day and is taken with food or on an empty stomach. • The pioglitazone used in the alogliptin - pioglitazone combination therapy treatment group is pioglitazone hydrochloride and is a grey circular tablet. A 15 mg dose of this medication is administered once a day and is taken with food or on an empty stomach.

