Research Methods	
 • The change in the level of HbA1c will be compared among the 3 treatment groups – the glimepiride monotherapy treatment group, the alogliptin monotherapy treatment group, and the alogliptin - pioglitazone combination therapy treatment group – until the 24th week after the Baseline is taken. • CGMS will be checked to investigate changes in glycemic variability. • Glimepiride's nonproprietary name is glimepiride; this drug is a snowman shaped tablet. Starting with a 1 mg dosage once a day before the first meal, the investigators will decide to increase the dosage to a maximum of 2 mg in the Week 4. • Dosage adjustment will be conducted for participants proven to have persistent hyperglycemia (in the opinion of the investigator). • Alogliptin's nonproprietary name is alogliptin benzoate and is an oval-shaped yellow tablet. A 25 mg dose of this medication is administered once a day and is taken with food or on an empty stomach. • The pioglitazone used by the alogliptin - pioglitazone combination therapy treatment group is pioglitazone hydrochloride and is a grey circular tablet. A 15 mg dose of this medication is administered once a day and is taken with food or on an empty stomach. • The subjects will have their HbA1c level tested in Week 12 and Week 24 and will have their MAGE checked at the Baseline and in Week 24. • General characteristics (bodyweight and BMI), vital signs, and laboratory tests will be conducted in Week 4, Week 12, and Week 24. • MAGE will be measured using CGMS (continuous glucose monitoring system) for 3 days (72 hours). Education regarding eating, CGMS usage, notices, and correction will be given. • A follow-up safety survey will be conducted 30 days after the last visit.
Primary Selection Criteria	
<Selection Conditions>
 
 • Subjects selected for this trial will be male and female outpatients 19 – 80 years of age (by date of birth) with type 2 diabetes and with HbA1c levels of $7.5\% \leq \text{HbA1c} \leq 10\%$. • Patient's body mass index must be greater than 18 kg/m^2. • Subjects selected for the trial are patients who are starting treatment for the first time or who have failed with more than 8 weeks of treatment with 1,000 mg or the maximum tolerance dose (MTD) of metformin and want to change their medication.
Primary Exclusion Criteria	Exclusion Criteria>

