Accordingly, any changes in blood glucose levels, diabetes index, and related factors that occur in this trial when glimepiride, the most widely used sulfonylurea drug, the DPP-4 inhibitor alogliptin, and a combination therapy of alogliptin and pioglitazone are administered to Korean diabetes patients will be investigated.

Hypothesis:

The effectiveness (efficacy) of treatment with alogliptin, low dose glimepiride, and alogliptin - pioglitazone combination therapy will not be identical.

Primary Goal/Objective

The change in HbA1c from baseline at week 24 in treatment groups (the glimepiride monotherapy treatment group; the alogliptin monotherapy treatment group; and the alogliptin - pioglitazone combination therapy group.)

Secondary Goals/Objectives

- The change in HbA1c from baseline at week 12 and FPG levels from baseline at week 12 and 24.
- The change in parameters of glycemic variability assessed by CGM from the Baseline at week 24
- The change in lipid profile from baseline at week 12 and 24

7. Code Names (and Nonproprietary Name of Main Ingredients) of the Clinical Trial Drugs and Medical Devices, the Quantity of Active Pharmaceutical Ingredients, the Dosage, etc. (Including the Control Drug)

	Pioglitazone (Actos® Tablet)	Alogliptin (Nesina® Tablet)
Nonproprietary Name	Pioglitazone hydrochloride (pioglitazone)	Alogliptin benzoate (alogliptin)
Dosage	15mg	25mg
Quantity of Active Pharmaceutical Ingredients	16.53mg	34mg
Insurance Code	696300140	96300210
Vender	Takeda Pharmaceuticals Korea Co. Ltd.	Takeda Pharmaceuticals Korea Co. Ltd.
Description	White or light gray color convex cylindrical tablet	Pale yellow, oval-shaped, film coated tablet

Glimepiride (Amaryl® Tablet)	
Nonproprietary Name	Glimepiride
Dosage	1mg, 2mg
Quantity of Active Pharmaceutical Ingredients	1mg, 2mg
Insurance Code	Amaryl® Tablet 1mg – 652100790 / Amaryl® Tablet 2mg – 652100800
Vender	Handok Pharmaceuticals Co Ltd.
Description	
 
 
Amaryl® Tablet 1mg – Pale pink oblong tablet
  
 
 
Amaryl® Tablet 2mg – Green oblong tablet
  
 

8. Research Subject Selection Criteria, Exclusion Criteria, the Target Number Subjects and the Basis for This Calculation

1) Selection Criteria

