 - Glimepiride's nonproprietary name is glimepiride; this drug is a snowman shaped tablet. Starting with a 1 mg dosage once a day before the first meal, the investigators will decide to increase the dosage to a maximum of 2 mg in the Week 4.
 - Dosage adjustment will be conducted for participants proven to have persistent hyperglycemia (in the opinion of the investigator).

[figure not shown]
	Week 4	Week 12
--	---------------	----------------

Alogliptin 25mg	Dosage adjustment is not allowed	Dosage adjustment is not allowed
Glimepiride	1mg → 2mg	Dosage adjustment is not allowed
Alogliptin 25mg +Pioglitazone 15mg	Dosage adjustment is not allowed	Dosage adjustment is not allowed

- Alogliptin’s nonproprietary name is alogliptin benzoate and is an oval-shaped yellow tablet. A 25 mg dose of this medication is administered once a day and is taken with food or on an empty stomach.
 - The pioglitazone used by the alogliptin - pioglitazone combination therapy treatment group is pioglitazone hydrochloride and is a grey circular tablet. A 15 mg dose of this medication is administered once a day and is taken with food or on an empty stomach.
 - The subjects will test the HbA1c level in Week 12 and Week 24 and will check CGMS at the Baseline and in Week 24.
 - General characteristics (bodyweight and BMI), vital signs, and laboratory tests will be conducted in Week 4, Week 12, and Week 24.
 - MAGE will be measured using CGMS (continuous glucose monitoring system) for 3 days (72 hours). Education regarding eating, CGMS usage, notices, and correction will be given.
 - A follow-up safety survey will be conducted 30 days after the last visit.
 - Subjects will be enrolled in the trial for 6 months and following this a follow-up survey will be conducted.
 - Approximately 12 months will be required for the total trial period based on the last patient (6 months) to have their Baseline enrollment conducted.
 - Patients will be asked to come to the clinical research institution after Week 4, Week 12, and Week 24 (for Week 12 and Week 24, a period of ±7 days is permitted) after the Baseline (or the first) visit. In addition, patients will be requested to take a call 30 days after their last visit for the safety follow-up survey.
 - Subjects with a drug compliance of less than 80% will be eliminated.
 - Subjects with an HbA1c level of more than 9.0% in Week 12 will be eliminated.

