- Subjects who sign the trial subject consent form and participate in the trial but do not finish will be eliminated. The elimination of a subject can be determined at any time during the trial. Withdrawal of consent by the subject will also be considered as an elimination and the reason for the withdrawal of consent must be clearly recorded. Furthermore, if an adverse event and/or a serious adverse event occurs during the trial, the corresponding subject will be immediately eliminated from the trial.

Trial Flowchart

2) Comparison Group Selection and Random Assignment Method

All trial subjects who are eligible to participate will be randomly assigned and will receive a random assignment number. Subjects will be identified by their random assignment numbers in all procedures that are carried out after random assignment.

Samples will be assigned to Group A (glimepiride), Group B (alogliptin), and Group C (alogliptin-pioglitazone) by random assignment using the order in which patients consented to participate in the open-label trial. If the designated patient Baseline process is completed for each treatment group, the subject recruitment will end.

3) Trial Drug Administration · Dosage, Administration · Usage Methods, Combination Therapy, Reason for the Selection of the Control Drug Used

	Dose	Usage
Test Group A	Glimepiride 1mg (If necessary, increase in dosage to 2 mg possible until Week 4)	Oral administration of single dose once a day in the morning before eating
Test Group B	Alogliptin 25mg single dose (fixed dose)	Oral administration of single dose once a day in the morning before eating
Test Group C	Alogliptin 2mg + pioglitazone 15mg combination dose (fixed dose)	Oral administration of single dose once a day in the morning before eating

4) Details of Observation, Details of Pregnancy Test, Observational Test Methods

Table 1) Checklist of each patient visit during the trial period

	Screening and Baseline	Week 4	Week 12	Week 24	Safety F/U (Week 24 + 30 Days).
Permissible Visit Range	-	± 3 Days	± 7 Days	± 7 Days	± 3 Days
General Characteristics ¹⁾	O	O	O	O	
HbA1c	O		O	O	
MAGE (CGMS)	O			O	
Medical History	O				
Selection/Exclusion Criteria	O				
Vital Signs ²⁾	O	O	O	O	
Laboratory Tests ³⁾	O	SMBG/FPG	O	O	
Adverse Event	O	O	O	O	O

*Results from within 4 weeks of the screening and baseline tests can be used.

- 1) Sex, age, height (sex, age, and height will only be checked at the Baseline), bodyweight, BMI

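### The section 9.3 dosing table gives Group C alogliptin 2 mg, where every other dose statement in the protocol says 25 mg; almost certainly a dropped digit that should be corrected

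*Protocol*

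**What the plan says.** Protocol section 9.3 sets out the three arms in a table of dose and usage. The Group C row reads "Alogliptin 2mg + pioglitazone 15mg combination dose" and is marked as a fixed dose. The row above it, for Group B, reads "Alogliptin 25mg single dose", also fixed.

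The combination arm is described by dose in two other places, and both differ from section 9.3:

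- Research Outline, Trial Drug/Medical Device: "Alogliptin 25mg +pioglitazone 15mg"
- Section 9.1, dose-adjustment table: "Alogliptin 25mg +Pioglitazone 15mg", with no adjustment permitted at Week 4 or Week 12

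The running text on alogliptin in the Research Outline and in section 9.1 says "A 25 mg dose of this medication is administered once a day and is taken with food or on an empty stomach". The product table in section 7 lists one alogliptin product, with 25 mg in its dosage row.

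**The concern.** A fixed-dose arm cannot be both 2 mg and 25 mg. Section 9.3 is where a site would look up what each randomised group receives, and its table is the only one that sets group letters beside doses. The section 9.1 table is arranged by drug and carries no group letters.

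Two things would be at stake.

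- **The comparison.** Section 8.3 sizes the trial on alogliptin against alogliptin plus pioglitazone. That contrast measures the effect of adding pioglitazone only if both arms receive the same alogliptin dose. At 2 mg in Group C, the added drug and a lower alogliptin dose would be confounded. Group C enters two of the three pairwise comparisons, so the contrast with glimepiride would be affected as well.
- **Oversight.** Section 9.8 requires major protocol deviations to be reported to the IRB within 15 days and minor ones at least yearly. Read literally, correct dosing at 25 mg in Group C departs from the section 9.3 table, and a monitor would have to decide which section governs.

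**Working it through.** **Step 1: the plan's own calculation, to see whether the dose entry touches it.** The inputs are in section 8.3: α = 0.05/3 two-sided, power 0.9, SD 1.037 in both arms, mean changes −0.96 and −1.71 (difference 0.75).

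n per arm = (Z_α/2 + Z_1−β)² × (σ₁² + σ₂²) / (μ₁ − μ₂)²

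= (2.394 + 1.282)² × (2 × 1.037²) / 0.75²

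= 13.51 × 2.151 / 0.5625 ≈ 51.65, so 52 per arm.

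The protocol states 53, which agrees to within one patient. Power is 0.908 at 53 per arm and 0.961 at 66. Going from 53 to 66 implies dropout of 1 − 53/66 = 19.7%, and 3 × 66 = 198 as stated. No dose enters the formula, so correcting the entry changes none of these figures.

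**Step 2: every statement of the alogliptin dose, counting each once.**

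| Place in the Protocol | Alogliptin dose |
|---|---|
| Research Outline, Trial Drug list, alogliptin | 25 mg |
| Research Outline, Trial Drug list, combination | 25 mg (with pioglitazone 15 mg) |
| Research Outline, Usage and Dose | 25 mg |
| Research Outline, Research Methods | 25 mg |
| Section 7, product table, dosage row | 25 mg |
| Section 9.1, dose-adjustment table, alogliptin | 25 mg |
| Section 9.1, dose-adjustment table, combination | 25 mg (with pioglitazone 15 mg) |
| Section 9.1, text | 25 mg |
| Section 9.3, Group B | 25 mg |
| **Section 9.3, Group C** | **2 mg** |

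The count is nine to one. The alogliptin column in section 7 also shows 34 mg, but in the row for quantity of active ingredient, separate from the dosage row, so it is not a competing dose.

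**Step 3: is 2 mg a plausible regimen?** The ratio is 2/25 = 0.08, a 12.5-fold difference. The only listed product is a 25 mg tablet, described as "Pale yellow, oval-shaped, film coated tablet". The protocol mentions no other strength, no splitting and no titration for this arm. Both other statements of the combination dose give 25 mg.

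**Step 4: reach.** The row governs one arm, 66/198 = one third of the patients. That is the number the entry describes, not a number expected to be misdosed.

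**The case against.** The strongest reply is that the document already settles the dose. Section 9.2 defines Group C as alogliptin-pioglitazone. The Research Outline and section 9.1 give that combination as 25 mg plus 15 mg, and no 2 mg product is listed. A reader can therefore recover the right dose without the section 9.3 table, and nothing in the statistical design moves. That is correct, and it is why the point is a correction to the text and not a threat to the trial.

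A second reply is that one missing character in a table cell could have been lost when the PDF was read. The alogliptin insurance code in section 7 also appears one digit short of the other codes in that section. This cannot be excluded from the text alone. Against it, the rest of the Group C row is intact and the adjacent row kept its 25 mg. The possibility is a reason to look at the master page first.

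Third, the glimepiride timing and meal-timing wording in the same table is a separate and smaller matter. That is also right. Taking alogliptin before eating satisfies an instruction that allows it with food or on an empty stomach, so there is no contradiction there.

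**Conclusion.** The point holds. As printed, section 9.3 contradicts nine other statements in the same protocol, and 25 mg is the only dose consistent with the rest of the document. The discrepancy is 12.5-fold, in one of three arms. The effect on sample size, alpha and power is nil. Harm to patients or to the Group B versus Group C comparison would follow only if a site acted on the printed figure, which is unlikely. It should be fixed because it is a wrong dose in the operative dosing table.

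Two assumptions apply. The supplied text is taken to reproduce the protocol page faithfully. The dropped-digit explanation is an inference from the other entries, since the document cannot prove the cause.

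**What to change.** Check the Group C row against the approved master document, and against a source-language version if one exists. If it reads 2 mg there, change the entry in section 9.3 to alogliptin 25 mg plus pioglitazone 15 mg, fixed dose, and notify the nine sites.

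Two optional wording changes could go into the same correction:

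- For glimepiride, section 9.3 has "increase in dosage to 2 mg possible until Week 4", while section 9.1 places the increase at Week 4. Use the section 9.1 timing.
- Give one meal-timing instruction for Groups B and C.

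The cost is one line and a site notice, with no analytical or sample size consequence. Section 10.1 requires written IRB approval when the trial is altered, so the sponsor should settle whether this counts as an alteration or as an administrative correction. If it is an alteration, each institution's approval may be needed.
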